criteria	
 2. Prior use of bisphosphonates (Group 2 only) or sodium fluoride (doses for osteoporosis not for dental hygiene). 3. Hypocalcemia and hypophosphatemia: any value (age-matched) below the normal range at Visit 8 or 8A. 4. Vitamin D deficiency (serum 25-hydroxy vitamin D concentrations of < 20 ng/mL or < 50 nmol/L) at Visit 8 (Group 1) or Visit 8A (Group 2). 5. Renal impairment defined as an estimated glomerular filtration rate (GFR) < 60 mL/min/1.73 m² at screening based on the Schwartz formula at Visit 8 or 8 A; a serum creatinine above the normal range at Visit 9 (Group 1) or an increase between Visit 8A and Visit 9 greater than 0.5 mg/dL (44.2 µmol/L) for Group 2. 6. Female patients of child bearing potential are eligible only if they are not pregnant/non-lactating. Females of child bearing potential must be practicing a medically acceptable form of birth control for greater than 2 months prior to screening visit and consent to pregnancy tests during the study.
Study treatment	i.v. zoledronic acid (ZOL446) 5.0 mg/100 mL solution, supplied in a ready-to-infuse plastic bottle
Efficacy assessments	
The efficacy variables will be measured using the following techniques:
 
 • vertebral morphometric fractures • [REDACTED] • DXA measurements • bone marker analysis • [REDACTED] • bone age and metacarpal cortical width assessment • pain assessment
Key safety assessments	Adverse event monitoring, Physical examinations, Monitoring of laboratory markers in blood and urine; and bone safety monitoring.
Data analysis	
Data analyses will be performed separately for the two populations (Group 1 [SAF-1] and Group 2 [SAF-2]), if not otherwise specified.
 
For the patients in Group 2 (SAF-2); only descriptive statistics will be reported for the single treatment arm.

Key words	Osteoporosis, children and adolescents, zoledronic acid, chronic inflammation, Duchenne muscular dystrophy, glucocorticoids

1 Introduction

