3.6 Risks and benefits

Benefit

The potential benefit of zoledronic acid in children at risk of osteoporosis due to underlying disease or intermittent high dose GCs is outlined in [Section 1.1](#) and in the Investigator's Brochure.

[REDACTED]

Additional evidence suggests that bisphosphonates have anti-apoptotic effects on osteoblasts and osteocytes which may lead to increased trabecular thickness and thus, may partly explain why bisphosphonates produce a greater reduction in fracture risk than that expected from BMD gains alone (Plotkin 1999).

The skeletal toxicity of GC is confirmed in adults and children. Furthermore, BMD is greatly influenced by sex steroids, and puberty can be delayed in the presence of GC which can also result in short stature which may be offset by the use of bisphosphonates (Glorieux et al 1998).

Risks

Known risks of zoledronic acid

Since this protocol was first written in 2010, there have been more publications on the potential use of bisphosphonates in children with kidney diseases including nephrotic syndrome (Gruppen et al 2013, Sbrocchi et al 2011).

Zoledronic acid is concentrated and excreted via the kidney and, like other bisphosphonates, has the potential to produce renal injury. Thus, care should be taken when administering the compound to patients with renal insufficiency. Although case reports have been published in adults regarding the nephrotoxicity of zoledronic acid with an incidence of acute kidney injury (AKI) between 9% and 13%, bisphosphonate-induced AKI in children remains undocumented (Patzer 2008).

- In this protocol, patients are excluded if they have an estimated glomerular filtration rate (GFR) < 60 ml/min/1.73 m². In addition patients considered for Group 2 who have nephrotic syndrome with osteoporosis, who do not meet this exclusion criterion, have been stable for 3 months prior to enrollment, and meet the remaining eligibility criteria, can be considered for this study.

Post-infusion acute phase reactions are more common after the first infusion and can include pyrexia, muscle and joint pain,

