4.1 Inclusion criteria

Patients eligible for inclusion in this study have to fulfill all of the following criteria:

- Written informed consent must be obtained before any assessment is performed. An assent needs to be provided in accordance with ICH and local regulations.

Group 1:

1. Children and adolescents, male or female, between 6 to 19 years of age who met the inclusion criteria for entry into the Core study and who took at least one dose of study drug and have completed Visit 8 of the CZOL446H2337 Core study.
2. Patient must be enrolled into the extension at Visit 9 up to 10 months after Visit 5 (month 6) of the Core study.
3. Patients who followed the regimen of calcium and vitamin D intake as required in the Core study (at least 1000 mg calcium for 6-8 years of age or at least 1300 mg calcium for 9-19 years of age and at least 600 IU daily vitamin D, through diet or supplementation).

Group 2:

1. Children and adolescents, male or female, between 5 to 17 years of age who met the inclusion criteria for entry into the Core study but were not enrolled because of clinically significant back pain from vertebral fracture and the preexisting clinical care at the Investigator's site is to treat this type of patient with a bisphosphonate.
2. Confirmed diagnosis of non-malignant conditions (including but not limited to rheumatic conditions, inflammatory bowel disease, Duchenne muscular dystrophy, nephrotic syndrome) who have stable normal renal function for at least 3 months prior to screening or

other subtype of secondary osteoporosis in children taking GCs, except patients with oncologic conditions (such as lymphoma and leukemia) see [Appendix 6](#)), treated with systemic GCs (i.v. or oral) within the 12 months preceding enrollment in the study (any duration)

3. Lumbar Spine areal BMD Z-score of - 0.5 or worse confirmed by central imaging
4. Evidence of at least 1 vertebral compression fracture (at least Genant Grade 1 vertebral compression or radiographic signs of vertebral compression*) seen on X-ray within 1 month of or at screening visit confirmed by central reading.

*Radiographic signs of vertebral compression fracture include loss of endplate parallelism, vertebral buckling and endplate interruption.

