4.2 Exclusion criteria

1. Patients who demonstrated a major protocol violation in the Core study (Group 1 only)
2. Patients for whom the investigator considers participation in the Extension study is not appropriate (Group 1 only).

(For both groups)

3. Hypocalcaemia and hypophosphatemia: any value (age-matched) below the normal range at Visit 8 or 8 A.
4. Vitamin D deficiency (serum 25-hydroxy vitamin D concentrations < 20 ng/mL or < 50 nmol/L) at Visit 8 for Group 1, Visit 8 A for Group 2.
5. Local serum ionized calcium below the normal range at Visit 9.
6. Renal impairment defined as an estimated GFR < 60 ml/min/1.73 m² based on the Schwartz formula at screening Visit 8 or 8 A (in the case of DMD additional methods may have been recorded in the source documents). Serum creatinine above the normal range at Visit 9 (Group 1) or an increase between Visit 8 A and Visit 9 greater than 0.5 mg/dL (44.2 μ mol/L) for Group 2.
7. Uncontrolled symptoms of cardiac failure or arrhythmia
8. Any prior use of bisphosphonates (other than study drug during the Core study for Group 1 only) or sodium fluoride (doses for osteoporosis not for dental hygiene).
9. Current active hyperparathyroidism or hyper/hypothyroidism or during the Core study.
10. New diagnosis of sarcoidosis currently or during the Core study.
11. New malignancy diagnosis currently or during the Core study.
12. History of hypersensitivity to any of the study drugs or to drugs of similar chemical classes.
13. History of primary bone disease (OI, idiopathic juvenile osteoporosis, rickets/osteomalacia).
14. Female patients of child bearing potential are eligible only if they are: (1) not pregnant/non-lactating; (2) are sexually abstinent or are surgically sterile or (3) if sexually active, must be practicing a medically acceptable form of birth control for greater than 2 months prior to screening visit.

- Females of child bearing potential who are sexually active must agree to continue to practice their birth control during the trial and at least 1 year after completing the trial and must consent to a pregnancy test prior to every dose administration and at the End of Study (EOS) Visit.

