Visit	8A	9	10	11	12	13	14	15/EOS and TD and/or PSW	Screening period from Visit 8A to Visit 9 should be as close to 28 days as possible, but cannot be longer than 8 weeks
Months relative to the Core study (after Visit 9 - Baseline of Extension study)		28 days from V8A	10 days after V9	3 months after V9	6 months after V9	10 days after V12	9 months after V9	12 months after V9	
Obtain informed consent (D) and assent (S)	X								
Inclusion/exclusion criteria (S)	X	X							
Medical History (D)	X	X							
Prior/concomitant medication, including GCs (D)	X	X	X	X	X	X	X	X	
Vital signs (D)	X	X			X			X	Pulse and blood pressure
Physical examination (S)	X	X			X			X	Including an oral examination for exposed bone
Tanner staging (D), if applicable		X						X	
Weight (D)	X	X			X			X	
Pain assessment		X		X	X		X	X	Pain is assessed using Faces Pain Scale-Revised (FPS-R)
Central laboratory test (hematology, biochemistry including urinalysis)	X	[X]	X		X	X		X	All patients will have limited blood chemistry, GFR and urinalysis performed at Visit 10 and Visit 13. [Visit 9 lab draw only if more than 4 weeks from Visit 8A].
Serum creatinine (local lab)	X	X							For exclusion purposes
Ionized calcium (local lab)		X							Measured pre-dose (local lab) prior to first infusion

	Screening Visit	Infusion Visit ¹		Telephone	Infusion Visit		Telephone		Notes
Visit	8A	9	10	11	12	13	14	15/EOS and TD and/or PSW	
Bio-markers (Serum P1NP, NTX, BSAP, Trap-5b)		X			X			X	
Serum 25 hydroxy vitamin D	X							X	
Pregnancy Test	X	X		[X]	X			X	To be performed for females with childbearing potential only [Only for sites where additional safeguards are required: Supervised urine pregnancy test]
i.v. drug administration (zoledronic acid)		X			X				
Dispense calcium and vitamin D, if required	X	X			X				
DXA measurements (lumbar spine, total body and distal femur)	X				X			X	
X-ray	X							X	Lateral thoraco-lumbar spine and postero-anterior left hand/wrist
Adverse events and SAEs (D)	X	X	X	X	X	X	X	X	SAEs only collected between Visit 8A and Visit 9 (AEs during this time recorded as medical history)
Study completion								X	
S = Source data, D = Database, TD = study treatment discontinuation, PSW = premature patient withdrawal									

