6.5.4.2 Clinical chemistry

Non-fasting specimens will be obtained for glucose, creatinine, serum urea, uric acid, total protein, SGOT (AST), SGPT (ALT), alkaline phosphatase, sodium, potassium, chloride, phosphorus, magnesium, albumin, total bilirubin, gamma-glutamyl transpeptidase (GGT) and calcium.

Glomerular Filtration Rate (GFR) will be calculated using the Schwartz equation at all visits where serum creatinine will be measured (Visits 8A (Group 2 only) 9, 10, 12, 13 and 15) by the Central Laboratory.

Schwartz Formula to calculate Glomerular Filtration

$GFR (mL/min/1.73 m^2) = k [Height (m)] / Serum Creatinine (mg/dL)$

k = Constant

k=0.41

Specialized (non-fasting) testing for serum 25-hydroxy vitamin D will be performed at Visit 8/8A and Visit 15. Additional local laboratory evaluation of serum ionized calcium will be evaluated in the local laboratory at pre-dose (first infusion). If local serum ionized calcium at Visit 9 is less than the normal range, the infusion must not be given. The patient may retest once at the investigator's discretion. If the serum ionized calcium retest is in the normal range, the patient may be dosed.

Also, local laboratory evaluation of serum creatinine will be performed at Visit 8A (Group 2 only) and Visit 9 for exclusion purposes. If local serum creatinine at Visit 9 is less than the normal range, the infusion must not be given. The patient may retest once at the investigator's discretion. If the serum creatinine retest is in the normal range, the patient may be dosed.

Patients with laboratory tests containing clinically significant abnormal values will be followed regularly until the values return to normal ranges or until a valid reason for the abnormality, other than study drug related adverse event, is identified

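### For Group 2, the Visit 9 creatinine rule in exclusion 6 can pass a value above the protocol's own normal range at every age, and the other Visit 9 renal checks do not agree with it

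*Protocol*

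**What the plan says.** Exclusion 6 in protocol Section 4.2 has three renal limbs.

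- **Screening, both groups:** "Renal impairment defined as an estimated GFR < 60 ml/min/1.73 m² based on the Schwartz formula at screening Visit 8 or 8 A".
- **Visit 9, Group 1:** any serum creatinine above the normal range excludes.
- **Visit 9, Group 2:** only "an increase between Visit 8 A and Visit 9 greater than 0.5 mg/dL" excludes. Item 5 of the key exclusion criteria in the Protocol Summary says the same: "an increase between Visit 8A and Visit 9 greater than 0.5 mg/dL".

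Other places bear on the Group 2 child at Visit 9.

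- **Section 3.6** names the kidney as a known risk of the drug and gives the GFR exclusion as the safeguard: "patients are excluded if they have an estimated glomerular filtration rate (GFR) < 60".
- **Section 3.1** lets the Visit 8A central results stand for Visit 9 if they are no more than 30 days old. Otherwise a redraw is reviewed for eligibility.
- **Table 6-2** notes "Visit 9 lab draw only if more than 4 weeks from Visit 8A" for the central laboratory, and schedules local creatinine at Visits 8A and 9. Appendix 7 lists no central chemistry sample at Visit 9.
- **Section 6.5.4** lists central biochemistry and renal monitoring at Visit 9, and **Section 6.5.4.2** lists Visit 9 among the visits with a calculated GFR.
- **Section 6.5.4.2** also withholds the infusion if the local Visit 9 creatinine is below the normal range, with one retest allowed and dosing if the retest is normal.
- **Sections 4.1 and 4.2:** Group 2 covers "Children and adolescents, male or female, between 5 to 17 years of age". The exclusion based on the investigator's judgment is for Group 1 only, and investigators may add no exclusions of their own.

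**The concern.** An absolute rise of 0.5 mg/dL is large against paediatric creatinine values. If it is wider than a child's whole normal range, the Group 2 limb can pass a result that the protocol's own table calls abnormal and that the Group 1 limb would exclude.

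Two things are at stake. The first is eligibility. A child whose renal function has clearly worsened since screening could meet the written criteria for a renally excreted drug, in the group whose entry criteria expressly mention nephrotic syndrome with stable normal renal function. The second is interpretation. Section 9.4.1 singles out renal safety, and Section 6.2 allows Baseline 2 laboratory values to come from Visit 8A or Visit 9. Where the Visit 8A value is the baseline, a decline that preceded the infusion could be tabulated as a change after it.

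**Working it through.** **Plan's own figure.** 0.5 mg/dL x 88.4 = 44.2 µmol/L, which matches the conversion printed in exclusion 6. The threshold is not a unit slip.

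**Step 1: compare the rise with the normal ranges.** The inputs are the creatinine ranges in Table 13-1 (Appendix 1). The largest permitted Visit 9 value is Cr0 + 0.5, where Cr0 is the Visit 8A creatinine, because only a rise greater than 0.5 excludes. The ranges come from the central laboratory. The Visit 9 exclusion sample is local, and local ranges are not in the documents, so I assume they are similar.

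**Step 2: fractional fall in GFR.** Section 6.5.4.2 gives GFR = k x height / creatinine. At fixed height the fraction remaining is Cr0/(Cr0 + 0.5), so the fall is 0.5/(Cr0 + 0.5). Neither k nor the height unit matters.

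| Age band | Normal range (mg/dL) | Width | Range + 0.5 | Multiple of upper limit | Fall in GFR |
|---|---|---|---|---|---|
| 5-7 y | 0.2-0.5 | 0.3 | 0.7-1.0 | 1.4-2.0 | 71-50% |
| >7-10 y, girls | 0.2-0.6 | 0.4 | 0.7-1.1 | 1.2-1.8 | 71-45% |
| >7-10 y, boys | 0.3-0.6 | 0.3 | 0.8-1.1 | 1.3-1.8 | 62.5-45% |
| >10-13 y | 0.3-0.7 | 0.4 | 0.8-1.2 | 1.1-1.7 | 62.5-42% |
| >13-16 y | 0.4-0.8 | 0.4 | 0.9-1.3 | 1.1-1.6 | 56-38% |
| >16-20 y | 0.5-0.9 | 0.4 | 1.0-1.4 | 1.1-1.6 | 50-36% |

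No range is as wide as 0.5, so every normal starting value plus 0.5 exceeds its upper limit. The fall is more than half only if 0.5/(Cr0 + 0.5) > 0.5, that is, if Cr0 < 0.5 mg/dL.

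**Step 3: compare with the screening limit of 60.** To remain at or above 60 after a rise of 0.5, the screening GFR must be at least 60 x (Cr0 + 0.5)/Cr0. This is 210, 160, 120 and 93 for Cr0 of 0.2, 0.3, 0.5 and 0.9.

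Absolute values need a height, which is my assumption, and height in centimetres. With metres, as printed, 0.41 x 1.15/0.4 is about 1.2, which is not usable; that unit is a separate matter.

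- 115 cm, 0.4 to 0.9 mg/dL: 0.41 x 115/0.4 = 118, falling to 0.41 x 115/0.9 = 52.
- 165 cm, 0.8 to 1.3 mg/dL: 85 falling to 52, without halving.
- 110 cm, 0.2 to 0.7 mg/dL: 225 falling to 64, which is more than halved but still above 60.

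Halving (Cr0 < 0.5, so a Visit 9 value below 1.0) and falling below 60 occur together only if 0.41 x height/1.0 < 60, that is, below about 146 cm.

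**Step 4: what else could catch the child?**

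- The Section 6.5.4.2 hold, read literally, acts on low creatinine, so it does not. If the opposite direction was intended, it would hold a Group 2 child whom exclusion 6 admits, and the two sections would contradict each other.
- A Visit 9 GFR may not exist. Table 6-2 and Appendix 7 point to no central sample within 4 weeks of Visit 8A, while Sections 6.5.4 and 6.5.4.2 list one. Even where it exists, exclusion 6 ties the GFR limit to screening.
- The redraw in Section 3.1 is reviewed for eligibility, but only when the earlier sample is more than 30 days old.

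**The case against.** A reader might infer that exclusion 6 contradicts itself, that any passed child may have lost more than half of renal function, and that nothing else in the protocol could stop the infusion. The documents do not support these readings.

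- **Self-contradiction.** The limit of 60 is applied at Visit 8 or 8A. The Group 2 limb at Visit 9 is a separate change-from-screening test, and both can be applied as written. The groups also have different data: Table 6-2 gives Group 2 a local creatinine at both visits, while Table 6-1 gives Group 1 one at Visit 9 only. Different limbs are not wrong in themselves.
- **More than halved.** This needs a Visit 8A creatinine below 0.5 mg/dL. It covers nearly all of the normal range at 5-7 years and none of it above 16.
- **Nothing else catches it.** The hold in Section 6.5.4.2 closely follows the wording of the ionized calcium hold just before it, and its retest sentence allows dosing on a normal result. Its direction may be a drafting slip, in which case the defect is a clash between Sections 4.2 and 6.5.4.2. Section 5.6.2 requires treatment to stop where there is a safety risk, and Section 11.1 expects immediate safety action even if it is a deviation. Meeting the criteria therefore does not oblige anyone to dose.

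Exposure is also limited. Screening lasts about 28 days, Section 4.1 asks for stable normal renal function for 3 months (at least in nephrotic syndrome), and Appendix 6 disallows chronic kidney disease. The primary objective concerns Group 1 and Group 2 is summarised descriptively, so no hypothesis test is affected.

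These points narrow the concern but do not remove it. The general safety clauses set no creatinine limit, and the written Group 2 rule still passes values that Table 13-1 calls abnormal.

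**Conclusion.** The concern holds in this form: followed as written, the Group 2 limb of exclusion 6 lets a child with a normal screening creatinine reach 1.1 to 2.0 times the Table 13-1 upper limit at Visit 9 without being excluded, in every age band, where the Group 1 limb would exclude. The associated fall in Schwartz GFR runs from 36% to 71%. Some children can pass below the screening limit of 60, which is incoherence between visits. Separately, the sections describing the other Visit 9 renal checks disagree on the direction of the hold and on whether central tests and a GFR are available.

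The comparison with the upper limits rests on local ranges resembling Table 13-1. The percentage falls rest only on fixed height. The absolute GFR examples rest on assumed heights in centimetres. The documents give no basis for estimating how often such a rise would occur.

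**What to change.** Reconcile the Protocol Summary (key exclusion 5), Section 4.2 (exclusion 6), Table 6-2, Sections 6.5.4 and 6.5.4.2, and Table 13-1 so that one consistent Visit 9 renal eligibility rule applies to Group 2. In the same amendment, correct or confirm the direction of the creatinine hold in Section 6.5.4.2, and state whether a Visit 9 GFR is available when the Visit 8A central results are carried forward. Which rule applies is for the sponsor to decide; no threshold is proposed here.

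The cost is a short amendment and an updated eligibility checklist. The local Visit 9 creatinine is already drawn, so that part needs no extra sample. The small downside is that a Group 2 child may occasionally be deferred or screen-failed.

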5.1 Study treatment

5.1.1 Investigational and control drugs

Zoledronic acid 5.0 mg/100 ml solution supplied in a ready-to-infuse plastic bottle, twice yearly.

5.1.2 Additional treatment

Adequate intake of vitamin D and calcium is mandatory for the four weeks prior to randomization and throughout the duration of the study, either through adequate dietary intake or via supplementation, or a combination of both diet and supplementation. Described below are the recommended guidelines for vitamin D and calcium intake. It is the responsibility of the investigator to ensure that each patient receives the adequate recommended daily allowance (RDA) of vitamin D and calcium (through diet and/or supplementation)([Ross et al 2011](#)).

Table 5-1 Recommended minimum daily dietary allowances

Age	Vitamin D	Calcium
≥ 5 years to ≤ 8 years	600 IU	1000 mg
≥ 9 years to ≤ 20 years	600 IU	1300 mg

All patients should take at least 600 IU vitamin D daily from Visit 8/8A until the final extension study visit through diet and/or supplementation.

Elemental calcium, at least 1000 mg for 5-8 years of age or at least 1300 mg for 9-20 years of age, daily will be taken beginning at Visit 8/8A and during the total duration of the trial, through diet and/or supplementation. Calcium carbonate is the preferred form of calcium

supplementation. If calcium carbonate is not well tolerated, another form of oral calcium would be acceptable.

Any vitamin D and calcium supplements will be recorded on the Concomitant medications/Significant non-drug therapies eCRF.

In addition, transient hypocalcemia has been reported following the first infusion and it can cause symptoms in rare cases. To prevent the development of symptomatic hypocalcemia, the parent or legal guardian of each child will receive an information sheet and all patients will receive calcium supplementation at the doses recommended in [Table 5-1](#) starting at least from the day of infusion and for a minimum of 5 days after the infusion (for sites where this calcium supplementation usually starts prior to the infusion, the total treatment period is approximately 10 days in total) ([Hogler et al 2004](#)).

5.2 Treatment arms

All patients will be given open-label zoledronic acid.

